2 OBJECTIVES

The objective of the study is to compare the rate of tear evaporation, measured with a novel evaporimeter, before and after DAILIES TOTAL1 and Biotrue ONEday CLs are worn in symptomatic and asymptomatic contact lens wearers.

The primary outcome variable for this study are the slopes calculated from the change in relative humidity over time.

Other variables of interest include:

- Contact lens dry eye questionnaire-8 (CLDEQ-8) score
- Comfort (subjective rating)
- Dryness (subjective rating)
- Non-invasive break up time
- Lipid layer thickness (Tearscope, LipiView II)
- Ocular surface area (mm²)
- Volume inside the goggle (cm³)

3 HYPOTHESIS

The study hypothesis is that there will be a higher rate of tear evaporation with CL wear compared to when CLs are not worn.

There will also be a significant difference in the rate of tear evaporation of DAILIES TOTAL1 (DT1) and Biotrue ONEday (BOD) after a minimum of 6 hours of CL wear.

There will also be a higher rate of tear evaporation in symptomatic contact lens wearers compared to asymptomatic lens wearers.

4 MATERIALS AND METHODS

4.1 STUDY DESIGN

4.1.1 OVERALL DESIGN

[figure not shown]
This study is a prospective, double-masked (investigator and participant), contralateral, non-dispensing study. Each participant will be randomized to wear DT1 in one eye and BOD in the fellow eye. Both lenses will be worn on a daily wear basis. This study will involve 3 scheduled visits over 2 days.

Visit 1: Screening and contact lens fitting visit

Visit 2: Baseline dispensing visit with BOD and DT1 lenses (morning visit)

Visit 3: Follow up visit with BOD and DT1 lenses (afternoon visit)

Visit 2 (baseline visit) and Visit 3 (follow up visit) will be conducted on the same day. There will be 5.5 hours \pm 30 minutes between Visit 2 and Visit 3, during which time participants are not required to remain at the School of Optometry & Vision Science.

4.1.2 RANDOMIZATION

A randomization schedule will be generated using a web-based program: (www.randomization.com). Participants will be randomized to the type of contact lens to be worn in each eye at Visit 2. A separate randomization will be generated for symptomatic and asymptomatic participants. The final study randomization schedule will be generated by CORE's Database Administrator, and provided to the research assistants for the study. Study investigators will remain masked to the randomization schedule until the interim data analysis. Study investigators will be granted access to the randomization schedule for the first 10 symptomatic and 10 asymptomatic participants in order to conduct the interim data analysis. Following

calculation of the sample size required to complete the study, study investigators will remain masked to the remainder of the randomization schedule until the study is completed and the database is locked.

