4.1.3 MASKING

Participants will be masked to the brand of contact lens worn in each eye at Visit 2 and Visit 3. In order to mask the participant, a research assistant will transfer the lenses and blister pack solution directly from the blister packs and will place them in a contact lens cup. The investigator will be masked as much as possible; however, it may not be possible to fully mask the investigator, because identifying lens markings may be visible during the biomicroscopy examination.

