4.5.18 LIPID LAYER THICKNESS (KEELER TEARSCOPE)

The participant will be seated at a slit lamp and a diffuse white light will be shone onto the participant's eye. Lipid layer thickness will be graded according to the interference pattern observed based on Guillon and Guillon's classification system⁷ (open meshwork, closed meshwork, wave, amorphous, colour fringe, and other).

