10 STATISTICAL ANALYSIS AND DATA MANAGEMENT

10.1 STATISTICAL ANALYSIS

All data will be analyzed by CORE at the University of Waterloo on unmasked data using Microsoft Excel and statistical analysis software such as GraphPad and SPSS. Interim data analysis will be conducted after 10 symptomatic and 10 asymptomatic participants have completed the study to determine the optimal time period over which to calculate the slope. The results of the interim data analysis will also be used to calculate the sample size.

Descriptive statistics will be provided on information regarding baseline variables (age, sex, contact lens refractive error distribution, etc.). Data may be evaluated for individual groups

(asymptomatic versus symptomatic) and when both groups are combined. Data will be tested for normality of distribution using Shapiro-Wilk tests. A p -value of < 0.05 will be considered statistically significant. Additional analysis may be conducted.

Table 4 lists the primary outcome variables and anticipated statistical procedures.

Table 4: Outcome variables and anticipated statistical procedures

| Variable | Analysis | Statistical test |
|--------------------------------------------------------------------------------------------------------------------------------------------------------------|--------------------------------------------------------------------------------------------------------------------|--------------------------------------------------------------------------------------------------------------------|
| Tear evaporation rate | Change in relative humidity over time | Slope |
| Tear evaporation rate/Time | Effect of lens type | RMANOVA Mauchly's test of sphericity Greenhouse-Geisser p values Tukey HSD post hoc Paired t -test |
| Tear evaporation rate/ Subjective ratings/Non- invasive breakup time/Lp d ayer thickness (Lp View II - continuous)/Area of the ocular surface | Relationship between tear evaporation rate and subjective comfort and dryness/other tear film assessments | Pearson correlation – r |
| Tear evaporation rate/ Lp d ayer thickness (Tearscope - ordinal)/ Volume of the goggle | Relationship between tear evaporation rate and lpdayer thickness | Spearman correlation – ρ |

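### At the interim, study investigators receive the lens codes of the first 20 participants; neither interim task needs brand identity, and nothing separates them from those who measure later participants (at most 30)

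*Combined protocol and SAP*

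**What the plan says.** Section 4.1.1 describes a "double-masked (investigator and participant), contralateral, non-dispensing study". Under section 4.1.2 the Database Administrator generates the schedule, research assistants hold it, and investigators are masked up to the interim. At that point: "Study investigators will be granted access to the randomization schedule for the first 10 symptomatic and 10 asymptomatic participants". The reason given is the interim analysis. Once the sample size has been calculated, "study investigators will remain masked to the remainder of the randomization schedule until the study is completed and the database is locked".

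Section 4.1.3 limits the claim of masking: "it may not be possible to fully mask the investigator, because identifying lens markings may be visible during the biomicroscopy examination".

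Section 10.1 gives the interim two tasks. One is "to determine the optimal time period over which to calculate the slope"; the other is the sample size, which section 4.2.1 assigns to G*Power. Section 10.1 also says that analysis is done on unmasked data.

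Two tear film measures rest on the investigator's eye. Section 4.5.17 times break-up by watching for the first dark spot through the Tearscope, and section 4.5.18 says "Lipid layer thickness will be graded according to the interference pattern observed".

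**The concern.** One role, the study investigators, is unmasked for 20 participants and then expected to act as a masked role for the rest. The plan names no separate interim analyst and no separate assessor.

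Concealing the later codes protects less than it seems to. An investigator who notices a lens marking before the interim learns the brand. After the interim, the same glimpse can be joined to knowledge of which brand was ahead. That expectation could colour a hand-timed break-up reading or the choice between neighbouring lipid patterns. Data collected before and after the interim would then have been gathered under different conditions of masking.

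What is at stake is the credibility of the investigator-judged secondary variables and of the double-masked label. The sensor slope is not the main exposure.

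**Working it through.** The plan states no sample size, effect size, SD or power, so it offers no figure to reproduce. The check has four parts.

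1. **How many participants come later.** Section 4.2.2 caps randomization at 50, and section 4.2.1 places the interim after 20 completers. The most that can follow is 50 − 20 = 30, or 30/50 = 60% of the total. Screening is also capped at 50, so reaching 30 requires no screen failures and no dropouts. With 40 participants in all, 20 follow; with 30, 10 follow. If the study stops at its minimum target of 20 completers, none follow.

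2. **Whether the brand could be recognised before the judged readings.** At Visit 3 (section 4.4.4), lens fit is assessed first, and section 4.5.9 does this at the slit lamp. Evaporimetry, break-up time and lipid grading come afterwards. Visit 3 is also the time point of the lens hypothesis in section 3. At Visit 2 (section 4.4.3) the fit check follows the readings. The route is therefore open at the visit that matters most for comparing lenses.

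3. **Whether the slope window needs the brand.** It is chosen from humidity against time. A criterion based on the traces themselves needs no lens label.

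4. **Whether the sample size needs the brand.** Let D be the DT1 − BOD difference within a participant, with mean m and standard deviation s. Under one recode applied to every participant, X − Y equals either D throughout or −D throughout.
   - SD(X − Y) = s in both cases.
   - |mean(X − Y)| = |m| in both cases.
   - The standardized difference |m|/s is therefore unchanged, and so is any two-sided paired sample size.
   - Section 3 gives no direction for the lens hypothesis, so the sign is not needed. The other two hypotheses (lens against no lens, symptomatic against asymptomatic) do not depend on brand.

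The recode must be consistent. If labels were removed altogether and only right-minus-left differences used, random allocation to eyes would make the expected mean about zero and inflate the variance to s²(1 + dz²), where dz = m/s, assuming no systematic right/left effect. With assumed dz = 0.5, two-sided 5% and 80% power, the paired t-test needs 34 participants using the true SD. With the SD inflated by √1.25 = 1.118 it needs 42, and a target difference would have to be fixed in advance. The X/Y recode avoids both problems.

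The direction that investigators would learn also rests on thin data. In simulated interims of 20 participants with assumed true dz = 0.2, the observed dz has a 95% range of −0.25 to 0.70, so the sign itself could be wrong. With true dz = 0.5 the range is 0.06 to 1.06.

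**The case against.** The case against is substantial, and much of it stands.

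- **The release is open and limited.** Later codes are concealed until lock, and section 4.1.3 already admits incomplete investigator masking. This stands. But an admitted chance of seeing the brand is a reason to withhold the interim direction.
- **The primary outcome is instrumental.** This stands. Table 4 assigns the lens-type tests only to tear evaporation rate; break-up time and lipid layer thickness appear only in correlations with it. A reader might infer an inflated false-positive rate for a lens comparison. No such comparison of these variables is listed, although section 10.1 allows additional analyses, and any rate would rest on an invented size of assessor shift.
- **A reader might infer that investigators could selectively repeat evaporimetry readings.** Section 4.5.16 fixes three consecutive open-eye and closed-eye measurements, and section 1 says that the goggle measures both eyes at once. The text offers no discretionary repeat of one lens.
- **The same individuals may not do both jobs.** This stands as a limit. Section 4.1.2 unmasks a role and section 4.5.17 has the investigator viewing the tear film, but the documents neither equate nor separate the people.
- **Some expectation exists anyway.** The introduction links higher water content with dryness and contrasts the two lenses on water content. The interim adds to that expectation; it does not create it from nothing.
- **X and Y can be decoded.** Anyone who recognised one lens among the first 20 could match it to that participant's code and unlock the file. This is right, so recoding alone is not enough.

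**Conclusion.** The point holds as a weakness in role separation at the interim. Investigators are given brand identity that neither interim task requires, and are then described as masked for at most 30 further participants. The plausible harm is confined to Tearscope break-up time and Tearscope lipid grading. It depends on two conditions that the documents leave open: that the same people analyse and measure, and that the brand is sometimes recognised. No error rate or bias can be given from the documents.

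Two stronger readings should be resisted. The plan does not unmask the whole trial, because the remaining codes stay concealed. Nor can one say that the revealed codes give away the next ones: that depends on block size, which is not stated. If blocks were used, 10 revealed codes in a stratum would leak nothing with blocks of 2 or 10, while blocks of 4 would let the next code be guessed correctly with probability 0.67.

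This is a modest point, worth acting on because the remedy costs almost nothing and brings section 4.1.2 closer to section 4.1.1.

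**What to change.** In section 4.1.2, replace investigator access to the schedule with text to this effect:

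*For the interim analysis the Database Administrator will supply a file in which the two lenses are recoded Lens X and Lens Y, consistently across all participants and both symptom groups, and will keep the key until database lock. The slope window will be chosen without lens labels. The sample size will be calculated from the recoded file by a person who does not take or grade study measurements. Those who take or grade measurements will not receive the recoded participant-level file or any lens-level interim result; they will be told only the chosen window and the required number of participants.*

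Section 10.1 should be aligned so that its statement about unmasked data does not cover the interim.

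The cost is a wording change and one recoded column, with no added visits. Someone who does not measure must run the calculation; the documents do not show whether such a person is already on the team. Investigators would not learn the direction of the lens effect until lock, a small loss because the interim decisions do not use it.

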4.1.3 MASKING

Participants will be masked to the brand of contact lens worn in each eye at Visit 2 and Visit 3. In order to mask the participant, a research assistant will transfer the lenses and blister pack solution directly from the blister packs and will place them in a contact lens cup. The investigator will be masked as much as possible; however, it may not be possible to fully mask the investigator, because identifying lens markings may be visible during the biomicroscopy examination.

4.2 STUDY POPULATION

4.2.1 SAMPLE SIZE CALCULATION

Because this is a pilot study, a sample size calculation has not been completed. An interim data analysis will be undertaken after 20 participants (10 symptomatic and 10 asymptomatic) have completed the study. The results of the interim data analysis will be used to calculate a sample size using G*Power.

A p-value of < 0.05 will be considered statistically significant.

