4.2.2 NUMBER OF PARTICIPANTS

Up to 50 participants will be screened using CORE records and advertising approved by the UW Office of Research Ethics. Up to 50 participants will be dispensed/randomized with study products, with a target of at least 10 symptomatic and 10 asymptomatic participants completing the study. Informed consent will be obtained for all participants prior to their enrolment in the study.

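### The final sample size is to come from unmasked interim results in 20 participants, with no stated sizing input, target difference, power or stopping rule, so the size is largely left to chance and the type I error cannot be known

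*Combined protocol and SAP*

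**What the plan says.** Section 4.2.1 gives no starting calculation: "Because this is a pilot study, a sample size calculation has not been completed". It then plans the interim, "An interim data analysis will be undertaken after 20 participants (10 symptomatic and 10 asymptomatic) have completed the study", and derives the size from it: "The results of the interim data analysis will be used to calculate a sample size using G*Power". Section 10.1 repeats this, "The results of the interim data analysis will also be used to calculate the sample size", and gives the interim a second job, choosing the time window for the slope.

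The interim is unmasked. Section 4.1.2 states "Study investigators will be granted access to the randomization schedule for the first 10 symptomatic and 10 asymptomatic participants", and section 10.1 states "All data will be analyzed by CORE at the University of Waterloo on unmasked data". Section 4.1.2 also makes clear that the same study then carries on, with the rest of the schedule still masked.

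Section 4.2.2 sets the limits: at least 10 symptomatic and 10 asymptomatic completers, and "Up to 50 participants will be dispensed/randomized with study products". The significance criterion is "A p-value of < 0.05 will be considered statistically significant", with no adjustment for the interim.

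The plan does not state the power, the difference to be detected, whether the effect or only the SD enters G*Power, which of the three hypotheses in section 3 is sized, what happens if more than 50 are needed, or whether the first 20 are left out of the final test.

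**The concern.** An effect size observed in 20 pairs is a poor basis for sizing a trial. A chance high value ends recruitment early, and a chance low value sends the study to its cap. If the same 20 participants then count in the final test, the sample size depends on the data being tested and the 0.05 criterion need not hold its level. What is at stake is whether the size reflects a difference worth detecting or luck in the first 20, and whether a final p-value just below 0.05 means what it appears to mean.

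**Working it through.** **Inputs.** From the plan: 20 participants at the interim (4.2.1), paired lens comparison within participant (4.1.1), limits of 20 and 50 (4.2.2), alpha 0.05 (4.2.1, 10.1). Assumed, because the plan gives none: two-sided test, 80% power, and a true standardised paired difference dz (mean difference divided by the SD of the differences) of 0.5, with 0.3 to 0.65 as a range. The plan has no sample size figure to reproduce.

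**1. Size needed.** Take the smallest n for which a paired t-test has power of at least 0.80, using the noncentral t with n−1 df and noncentrality dz√n. At dz = 0.5, n = 33 gives 0.795 and n = 34 gives 0.808, so 34 are needed. Inverting the formula, the calculation returns 20 or fewer when the dz entered is at least 0.660, and more than 50 when it is below 0.404.

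**2. Sizing from the observed effect.** Observed dz × √20 follows a noncentral t with 19 df. At dz = 0.5 the noncentrality is 0.5 × 4.472 = 2.236.
- P(20 or fewer) = P(|t| ≥ 0.660 × 4.472 = 2.95) = 0.27.
- P(more than 50) = P(|t| < 0.404 × 4.472 = 1.81) = 0.33.

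| True dz | N needed | Interim calls for ≤20 | Interim calls for >50 |
|---|---|---|---|
| 0.3 | 90 | 8% | 66% |
| 0.4 | 52 | 15% | 50% |
| 0.5 | 34 | 27% | 33% |
| 0.65 | 21 | 50% | 14% |

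At dz = 0.5 the unrestricted interquartile range is 19 to 67. Held within the plan's limits it is 20 to 50, and 27% + 33% = 60% of interims land at one limit or the other.

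**3. Sizing from the SD only,** with the difference fixed in advance at 0.5 true SD. Here 19s²/σ² is chi-square with 19 df.
- 20 or fewer: s/σ ≤ 0.5/0.660 = 0.757, chi-square ≤ 19 × 0.573 = 10.9, probability 7%.
- More than 50: s/σ > 0.5/0.404 = 1.237, chi-square > 19 × 1.530 = 29.1, probability 6%.
- Interquartile range 27 to 40.

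**4. Type I error.** Simulation of at least 300,000 trials with no lens effect, first 20 included, final test at 0.05:

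| Rule after the interim | Type I error |
|---|---|
| Fixed 50, no re-sizing | 5.0% |
| N from observed effect, kept within 20–50 | about 6.4% |
| As above, and significance also claimed at 20 | about 8.7% |
| N from observed effect, but end at 20 if N > 50 | about 3.3% |
| N from SD only, kept within 20–50 | about 5.7% |

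As a check on the third row, a bivariate normal with looks at 20 and 50 (correlation √(20/50) = 0.632) gives 8.6%. The SD-only figure is 5.3% to 5.7% for fixed differences of 0.4 to 0.65 SD.

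**5. Power at dz = 0.5.** N from the observed effect within 20–50: 92%. The same, but ending at 20 if N > 50: 64%. SD-only: 81%.

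**The case against.** The study is a pilot, and that fairly explains why no size was calculated at the start. It does not remove the point, because section 3 states hypotheses and the same study is completed and tested at 0.05.

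A reader might infer that the plan says the observed lens effect will be entered into G*Power. It does not: 4.2.1 and 10.1 refer only to interim results. Opening the lens codes and naming no difference make that reading the likely one, but it remains a reading.

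A reader might also infer that the study may stop on a significant interim, with 8.7% as the plan's error rate. Section 10.1 gives the interim two purposes, the slope window and the sample size. No efficacy test or stop is described, and one equally possible rule takes the error below 5%.

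Quoting the unrestricted spread of the calculated size (10th to 90th percentile 14 to 175 at dz = 0.5) would overstate the practical effect, since section 4.2.2 keeps the study between about 20 and 50.

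Two further points stand. Effect-based sizing within the limits does not lose power on average at dz = 0.5 (92%); it behaves like an early-stopping design without the alpha control that such a design needs. And the type I gain from SD-only sizing is small, 6.4% to 5.7%. Choosing the slope window on the same unmasked data may matter more. If the window with the strongest lens result were taken (assumed 3 to 5 windows, correlation 0.5 to 0.8), type I error at n = 50 would be 7.7% to 11.6%.

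**Conclusion.** The concern holds as a gap in the sizing rule, and it is worth closing before the interim. The stronger half is instability: if the observed effect is used, the size mostly lands at 20 or 50 by chance when about 34 are needed. The weaker half is type I error, which runs from about 3.3% to 8.7% depending on a rule that the plan does not give; re-sizing alone accounts for about 6.4%. The documents support neither a claim that the plan certainly inflates the error rate nor a claim that it permits stopping on significance. All figures rest on an assumed two-sided test and 80% power, and the instability figures on dz = 0.5. The split between the two limits shifts with dz as tabulated, and at dz near 0.4 or 0.65 one limit is close to the right answer in any case.

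**What to change.** In sections 4.2.1 and 10.1:

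- Name the comparison being sized and the target power. The paired DT1 versus BOD comparison at Visit 3 is one candidate; section 3 does not rank the hypotheses, so the choice is the sponsor's.
- Fix the difference of interest before the interim, in a form that does not depend on the slope window, such as a percentage difference. Choose the window without reference to the lens effect.
- Enter into G*Power only the interim SD of the within-participant DT1 minus BOD difference, together with the pre-set difference. Do not enter the observed lens effect.
- Limit the size to 20–50. At 50 the paired comparison has 80% power only for dz of about 0.40 or more, and the plan should say so.
- State that no lens hypothesis is tested at the interim and that the study does not stop on significance.

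A masked right-minus-left SD may look like a way to avoid opening lens codes, but it is not a safe substitute. Each goggle lens has its own sensor (section 1). A constant left–right offset drops out of the right-minus-left SD but adds variance to DT1 minus BOD. In units of the SD without offset, the ratio of the two SDs at a lens effect of 0.5 is √[(1 + 0.25)/(1 + offset²)]: 1.12, 1.00 and 0.87 for offsets of 0, 0.5 and 0.8. It can therefore undersize the study.

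The cost is protocol wording and a difference that the team must commit to in advance. The planned size may come out larger.
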